# THO 1524: [F]FSPG PET Protocol

PET results (35). To date, in human studies, F-FSPG PET has been well tolerated, with no reported safety concerns (35).

#### 4. Patient Eligibility & Inclusion / Exclusion Criteria

Participants will be recruited by Vanderbilt University Medical Center and Tennessee Valley Health System Nashville (TVHS) study team members. Patient history will be reviewed for inclusion/exclusion criteria and informed consent obtained as described below.

Enrollment will be open to all patients of both genders with the above diagnoses described in the Specific Aims, with the following inclusion/exclusion criteria.

#### A. Inclusion Criteria

- 1. Adult patient (age 40 80).
- An indeterminate pulmonary nodule (IPN) (7–30 mm diameter) on CT, or an indeterminate lung mass (> 30 mm diameter), without prior examinations that establish that the lesion has been stable for two or more years.
- 3. Untreated.

#### OR

4. An adult patient with a newly diagnosed, untreated primary lung cancer diameter 7 mm or more.

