# Imaging Protocol: F-FSPG (Figure 1)

[figure not shown]
Each patient will undergo an SOC whole-body (vertex to mid thighs) F-FDG PET/CT scan within 60 working days of an F-FSPG PET/CT scan for these first 60 enrollees, with no intervening cancer treatment of the target lesion (limited biopsies or resections are allowed). A minimum of 12 hours must lapse between SOC (F-FDG) and F-FSPG PET/CT scans. Standard of care procedures performed prior to consent but within the protocol defined windows for each

assessment can be used for study purposes. All research only procedures must be performed after the consent date.

Eight (8) subjects with either indeterminate nodule(s) or thought or known to have newly diagnosed lung cancer, will receive an F-FSPG PET scan (emission only), acquired dynamically after injection over the nodule/mass of interest for 60 minutes, in order to characterize the time activity curves of F-FSPG. These 8 subjects will then have a short break (bathroom, stand up) and then receive a PET/CT scan from the vertex to the mid-thighs. This final body PET/CT covers the same anatomic range as the SOC F-FDG PET/CT, and will be compared closely to the F-FDG PET/CT to determine if there is added value of the F-FSPG PET/CT. Once the dynamic PET/CT scans with F-FSPG in the initial 8 subjects are obtained, the remainder of subjects will have a scanning protocol from vertex to mid-thighs about 60 minutes after F-FSPG injection, similar to the protocol for standard of care F-FDG PET/CT.

The third year will be used, if needed, to obtain at least two years of CT follow-up for patients with IPNs who chose serial follow-up CT scans over a tissue diagnosis (two years is required by Fleischner Society Guidelines to prove stability/benignity for solid nodules), though over 90% of malignant IPNs will demonstrate growth within one year by CT.

Figure 1: Flow Schema of Imaging:

\*Optional tissues collection noted in Figure 1 are part of separately enrolled study and not called for on this protocol.

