#### **11. Statistical Considerations**

#### **Study Design**

As we have shown from a large review of patients referred to us for IPNs and lung masses, F-FDG PET/CT has 92% sensitivity but 40% specificity for diagnosis of cancer, primarily due to inflammatory (especially granulomatous) lung nodules in our population. For F-FSPG to have a significant impact, we assume that the sensitivity of F-FSPG will be equal to F-FDG, but that the specificity of F-FSPG for the diagnosis of lung cancer will be 80%. Given the preliminary data we have shown with virtually no F-FSPG uptake in an active granulomatous abscess, we are very optimistic that our approach could succeed.

Our preliminary proposed investigation will include 30 subjects who had both PET scans done FDG and FSPG of patients meeting enrollment criteria and referred from the VUMC Pulmonary Medicine or Thoracic Surgical Oncology services. We will include those IPNs or lung cancers discovered *via* lung cancer screening or referred for a non-screened discovered IPN or cancer. If our preliminary data are encouraging, we will seek additional funding to enroll more to achieve statistical significance. However, we predict that we will need to extend the study to a total of 70 subjects completing a study to achieve significance. Our plans for the additional funding will be to approach the current IP holder (Piramal Life Sciences) as well as to apply for extra-mural funding with initial data from our initial subjects.

**Go/No-Go criteria:** To verify that data collected in this pilot imaging study supports proceeding to a larger efficacy trial, clear Go/No-Go criteria, which will be assessed at the end of enrollment and data analysis, have been established for each aim, and include:

A. Aim  $1 - {}^{18}$ F-FSPG PET/CT has equal sensitivity to  ${}^{18}$ -FDG PET/CT, with  $\ge 50\%$  specificity, compared to the proven 40% specificity of  ${}^{18}$ F-FDG PET/CT, for the diagnosis of indeterminate lung nodules, in our area with high endemic rates of fungal nodules.

B. Aim 2 –  $^{18}$ F-FSPG PET/CT is at least equivalent in overall accuracy to  $^{18}$ F-FDG PET/CT for staging of lung cancer.

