# Sample Size and Study Power

Because our study population will not originate solely from a lung cancer screening trial, it will be "enriched" for high risk of malignancy. Thus, the sample size calculation primarily focuses on the power to detect the minimum clinically important difference in the specificity of F-FDG and F-FSPG tests (19). Accordingly, comparing to F-FDG PET/CT scans, we hypothesize that use of the F-FSPG PET/CT will improve specificity for lung cancer diagnosis in our study population from 40% (F-FDG) to 80% (F-FSPG). We use McNemar's test for paired data to evaluate the specificity for these two methods. We assume the proportion of the discordant pairs is 0.2 and 0.6. A sample size of 37 benign subjects provides 80% power to detect a 40% increase in specificity with a two-sided type 1 error = 5%. Sixty-two subjects will be recruited to take the historic lung cancer prevalence of 0.4 (19) for the referral population to the pulmonary medicine or thoracic surgery services at VUMC for an IPN or lung mass. We will also apply a non-inferiority test to show that the sensitivity of F-FSPG is not worse than the F-FDG. A sample size of 25 cancer patients achieves 82% power at a 5% type 1 error using one-sided equivalence test when the sensitivity of F-FDG is 0.9 (42) and the maximum allowable difference between F-FDG and F-FSPG is 0.2. Thus, we propose to enroll up to 60 subjects to allow for possible dropout such as subjects lost to follow-up or choosing to withdraw from the study before protocol completion.

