# **Data Analysis**

As part of our "go/no go" analysis as initial proof of principle, we plan to enroll 30 subjects initially with IPNs or newly discovered lung masses, to determine if this initial enrollment will demonstrate a trend toward significance in accuracy for diagnosis of IPNs or lung masses. This will be an initial, "proof of principle" investigation. If not, we will consider other imaging probes. However, if we do see a trend of significance, we plan on 70 subjects to complete a study.

We will not know at time of enrollment if the subject has a benign or malignant IPN or mass. Historically, we have a 40% prevalence of cancer in our referral base, which, heretofore, is not a "screened" population. Thus, with 70 subjects completing a study, we expect that, after tissue confirmation or adequate clinical follow-up to establish benignity is established, to have about 42 subjects with benign nodules and 28 with cancer. The analysis of Specific Aim 1 will focus on the F-FSPG PET/CT's ability to discriminate up-front benign from malignant lung nodules/masses in all subjects. Analysis of Specific Aim 2 will then focus on analysis of known/confirmed lung cancers. Specific Aim 3 analysis will correlate the biomarker findings as described elsewhere in the Project Narrative with the findings of Specific Aims 1 and 2.

Sensitivity, specificity, overall accuracy and ROC curves will be generated and compared for both F-FDG and F-FSPG tests. Wilcoxon rank-sum or Kruskal-Wallis tests will be applied for the group comparisons of immunohistochemical staining (CD44 and  $x_c^-$  expression levels, Specific Aim 3) and the biodistribution characteristics of F-FDG and F-FSPG tests (Specific Aims 1 & 2). The demographic information such as age, smoking status/pack-year history will be tabulated. Descriptive statistics, including means, standard deviations, and ranges for continuous parameters (uptake expressed in SUVmax, SUVmean, SUVpeak) normalized to lean body mass and body weight, and ratios of these uptake values to cardiac blood pool and normal lung. as well as percentages and frequencies for categorical parameters, will be presented.

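### Already diagnosed lung cancers share the single subject count, yet the sample size and the Aim 1 analysis treat every subject as undiagnosed with 40% cancer prevalence

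*Combined protocol and SAP*

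**What the plan says.** Section 4 gives two alternative entry routes. Criteria 1–3 cover an untreated indeterminate nodule or mass. Criterion 4 covers "An adult patient with a newly diagnosed, untreated primary lung cancer diameter 7 mm or more". No quota or cap applies to either route.

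Other text confirms that both routes feed one count:

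- Section 11, Study Design, describes the 30 subjects that may extend to 70 and says "We will include those IPNs or lung cancers discovered" through screening or referral.
- Section 7, Imaging Protocol, lets the eight dynamic-scan subjects be "subjects with either indeterminate nodule(s) or thought or known to have newly diagnosed lung cancer".
- Exclusion 5 applies only to patients without a tissue diagnosis, which presumes that others have one.

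The statistical text reads differently. Sample Size and Study Power says "Sixty-two subjects will be recruited to take the historic lung cancer prevalence of 0.4", a prevalence it attributes to referrals for a nodule or lung mass. Data Analysis says "We will not know at time of enrollment if the subject has a benign or malignant IPN or mass", expects 70 completers "to have about 42 subjects with benign nodules and 28 with cancer", and directs Aim 1 at the tracer's "ability to discriminate up-front benign from malignant lung nodules/masses in all subjects".

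Section 2 limits Aim 1 to nodules and to masses that have not been biopsied. The Aim 1 Go criterion is worded "for the diagnosis of indeterminate lung nodules, in our area with high endemic rates of fungal nodules".

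**The concern.** Two consequences follow from mixing the entry routes.

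- **Specificity power.** Only benign subjects contribute to the specificity comparison, and a criterion 4 subject cannot be benign. Within a fixed total, each one replaces a subject who had an expected 0.6 chance of being benign.
- **Sensitivity, accuracy and ROC.** As Data Analysis is written, each criterion 4 subject adds a cancer proven before entry to the Aim 1 sensitivity denominator. Section 7, Clinical Data Analysis, has the readers un-blinded with the medical record available, so the known diagnosis can inform the read. That part of the estimate does not answer the question about indeterminate nodules.

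The Aim 1 Go decision requires sensitivity equal to FDG. Study Design says that insufficient sensitivity or selectivity contraindicates further study, so the composition of this set bears on whether the programme continues.

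**Working it through.** **Inputs from Section 11.** Discordant proportions 0.6 and 0.2; two-sided 5%; 80% power; 37 benign subjects; prevalence 0.4; totals 62 and 70. The criterion 4 share, k, is not in the documents, so 10%, 20% and 30% are assumed. Section 5 gives about 750 new nodules and 400 new lung cancers a year. If these groups were disjoint and recruited in proportion (an assumption), k would be 400/1150 = 35%.

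**1. The plan's own figures reproduce.** For McNemar's test let d = 0.6 − 0.2 = 0.4 and s = 0.6 + 0.2 = 0.8.

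- n = [1.96√s + 0.8416√(s − d²)]² / d² = [1.753 + 0.673]² / 0.16 = 36.8, so 37.
- Power at n = Φ((d√n − 1.96√s)/√(s − d²)). At n = 37 this is 80.2%.
- Total = 37/0.6 = 61.7, so 62. Cancers = 0.4 × 62 = 24.8, about 25.
- At 70: 0.6 × 70 = 42 benign and 0.4 × 70 = 28 cancers.

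All of these require k = 0.

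**2. Benign subjects and power with k above 0.** Expected benign = 0.6(1 − k)N.

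| k | N = 62: benign | power | N = 70: benign | power |
|---|---|---|---|---|
| 0 | 37.2 | 80% | 42.0 | 85% |
| 10% | 33.5 | 76% | 37.8 | 81% |
| 20% | 29.8 | 70% | 33.6 | 76% |
| 30% | 26.0 | 64% | 29.4 | 70% |

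Thirty-seven benign subjects are kept only if k ≤ 1 − 37/42 = 0.119 at N = 70, or k ≤ 1 − 37/37.2 = 0.005 at N = 62. Keeping 37 by raising the total would need 37/[0.6(1 − k)] = 69, 78 and 89 subjects at the three shares.

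**3. Dependence on the discordance.** With specificities of 40% and 80%, the values 0.6 and 0.2 are the largest discordant proportions possible. If the two tracers erred independently, they would be 0.8 × 0.6 = 0.48 and 0.2 × 0.4 = 0.08. Then 25 benign subjects give 80% power. Power stays at or above 80% up to k = 1 − 25/37.2 = 0.33 at N = 62, or 1 − 25/42 = 0.40 at N = 70.

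**4. Cancers proven before entry, as a share of all Aim 1 cancers.** k/[k + 0.4(1 − k)]:

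- k = 10%: 0.10/0.46 = 22%
- k = 20%: 0.20/0.52 = 38%
- k = 30%: 0.30/0.58 = 52%

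This depends neither on N nor on the discordance, so it applies equally to the first 30 subjects.

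**The case against.** **Reading.** In context, the reference to all subjects may only contrast benign plus malignant lesions (Aim 1) with known cancers (Aim 2). The same section describes the first 30 as having nodules or newly found masses, and Section 2 already limits Aim 1. This is a fair reading, but it does not rescue the counts: if Aim 1 means undiagnosed subjects only, the totals of 62 and 70 leave no room for the criterion 4 subjects counted in them.

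**Prevalence.** The historic 40% may itself include patients diagnosed before referral, in which case scaling by (1 − k) double-counts known cancers. The cited source cannot be checked here, so this stands as a caveat on the power figures. It does not help the sensitivity estimate. If 40% were the overall cancer share with known cases inside it, they would form k/0.4 of all cancers: 25% at k = 10% and 50% at k = 20%.

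**Size.** Under independent errors, power holds across the whole 10–30% range. The committed stage is 30 subjects, and no change in the Go decision at 30 has been shown. Known cancers reduce the precision of specificity without biasing it. All of this stands.

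**Blinding.** Un-blinded reading applies to every subject and both tracers, so it is partly a separate issue. That is true, but criterion 4 guarantees that a cancer diagnosis is already in the record at entry.

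**Consent timing.** Defining the set by status at entry makes membership depend on whether consent precedes biopsy. However, a lesion proven malignant before entry can still enter under criterion 4, while one proven benign has no entry route. Counting the former in Aim 1 enriches it in one direction only, and classifying at entry avoids this.

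**Conclusion.** The concern holds: the text is wrong as written and should be fixed. Eligibility, the imaging section and Study Design put diagnosed cancers in the single count, while the sample size and Data Analysis sections assume there are none.

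The loss of specificity power is conditional. It is 4 to 16 percentage points at N = 62 for k of 10–30% under the plan's discordance, and power need not fall below 80% if discordance is lower. This assumes that the 40% prevalence describes subjects entering under criteria 1–3. The firmer point is the composition of the sensitivity estimate: even at k = 10%, more than a fifth of its cancers would have been proven before entry. Specificity itself is not biased.

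**What to change.** 1. In Data Analysis, define the Aim 1 set as subjects entered under criteria 1–3 without a tissue diagnosis at study entry. Use it for Aim 1 sensitivity, specificity, accuracy, ROC curves and the Aim 1 Go criterion.
2. Fix that status at entry, so that a subject biopsied between the two scans, which Section 7 permits, stays in the set.
3. Record the entry route, and use criterion 4 subjects for Aims 2 and 3.
4. Restate the benign and cancer counts and the power for the criteria 1–3 subjects expected within the planned total, with the assumed k stated.

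**Cost.** The changes are wording and one data field. No extra subjects are needed if power is restated rather than the totals raised, but the stated specificity power becomes somewhat less favourable.

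Fewer cancers remain for Aim 1 sensitivity: 0.4(1 − k)N, which at k = 20% is 19.8 of 62 or 22.4 of 70, against the planned 25. At N = 70, 25 are kept only if k ≤ 1 − 25/28 = 0.107. The plan gives no discordance for the non-inferiority test. If total discordance of 0.15 is assumed, power is Φ(0.2√n/√0.15 − 1.645): about 83% at 25 cancers, 79% at 22.4 and 74% at 19.8. Pooling the criterion 4 cancers would raise it to about 90% at N = 62 (12.4 + 19.8 = 32.2 cancers), but partly on cancers that were never indeterminate at entry.

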#### AND

5. The patient must provide informed written consent, which will include a layman's explanation of the estimated amount of additional radiation that the patient will receive from the investigational PET/CT scan using F-FSPG.

6. The patient must agree at the time of study entry to undergo clinically indicated biopsy(ies) or a 24-month period of follow-up, as needed, to resolve the etiology of their IPN(s) or lung mass(es).

# **B. Exclusion Criteria**

- Pregnant or lactating patients will be excluded, as will females of childbearing potential who refuse to undergo a serum or urinary beta-HCG pregnancy test the day of either the F-FSPG or the F-FDG PET/CT scans, in accordance with the standard policy of the Medical Imaging Service at our facility. Women who have experienced 24 consecutive months of amenorrhea, have reached at least 60 years of age, or have had a tubal ligation or hysterectomy documented in their medical records are considered not to be of childbearing potential for the purposes of this protocol.
- 2. Patients with a body weight of 400 pounds or more or a body habitus or disability that will not permit the imaging protocol to be performed, due to the compromise in image quality on both CT and PET/CT. If the standard-of-care F-FDG/PET was of diagnostic quality as determined by the official clinical interpretation, then this will be presumptive evidence that

the patient's body habitus and/or disabilities should not prevent a diagnostic quality F-FSPG PET/CT scan, either.

- 3. A recognized active lung infection (this will confound the standard-of-care F-FDG PET/CT scan).
- 4. Previous systemic or radiation treatment for cancer of any type within 1 year.
- 5. For patients who do not have a tissue diagnosis:
  - A. Non-oncologic severe co-morbidities suggesting a life span of less than two years if not treated, as determined by the potential subject's treating physician.
  - B. If severe co-morbidities are present, the treating physician should indicate that a life span of 2 years is expected if treatments are effective.
  - C. This exclusion is to prevent loss of the needed 2 year CT follow-up to establish a benign diagnosis for lesions lacking tissue diagnosis if extremely fragile subjects are enrolled and then experience an untimely, unrelated death.

#### 5. Enrollment/Randomization

We propose a three (3) year funded prospective cohort with consecutive subject enrollment throughout each year. We will enroll subjects referred to the Oncology, Thoracic Surgery or Pulmonary Medicine Services at Vanderbilt University Medical Center and Tennessee Valley Healthcare System Nashville. We will allow a 2-year follow-up of all subjects to document stability by CT for IPNs that do not have a tissue diagnosis (stability on CT for two years of an IPN or mass is accepted presumptive evidence of benignity). Follow-up will be from the day of the baseline CT, and may be extended later if needed. At VUMC, we see about 750 patients with newly diagnosed IPNs annually, and about 400 patients with newly diagnosed lung cancer. Accordingly, given the high prevalence of granulomatous IPNs in our geographic region, we are well suited to perform the work we have described.

We will perform an analysis to correlate the F-FSPG PET/CT findings with F-FDG PET/CT and the surgical pathology results for the patients who have tissue correlation. Each subject will receive the "standard-of-care" F-FDG PET/CT as indicated for patients at high risk for lung cancer who have an IPN or lung mass meeting our size criteria, and will also receive the investigational F-FSPG PET/CT, with no intervening treatment of the target lesion(s). After enrolling 30 subjects, we will close enrollment but continue the study for data collection and analysis until the funding period ends and/or sufficient follow-up for diagnosis (up to 2 years) has occurred, and report our results in the peer-reviewed literature.

Should we achieve clear statistical superiority of F-FSPG PET/CT over F-FDG PET/CT before that time, we will pursue a larger trial to offer improved benefit of our patients for the diagnosis of IPNs and/or staging of lung cancer (*see* Go/No-Go criteria in Study Design). While 2 years' stability in nodule size is the "gold standard" for CT, well over 90% of cancers demonstrate growth on CT within one year. We will also perform the research outlined in Specific Aim 3 on tissue specimens obtained from our subjects in Specific Aims 1 and 2. If we find significant added value from the use of F-FSPG in either IPNs or lung cancer, we will propose further investigations.

Final diagnosis will be based on tissue biopsy (surgical or *via* a high-quality core biopsy) or negative (no growth) two-year follow-up with CT. We will assign patients with IPNs into the

"benign" category if their IPNs remain stable for two or more years, decrease in size, or resolve during CT follow-up, performed in accordance with Fleischner Society guidelines.

# **Patient Registration**

All patients MUST be registered with the Vanderbilt-Ingram Cancer Center (VICC) prior to the start of research procedures for all sites.

Patients will be centrally registered with the Vanderbilt-Ingram Cancer Center (VICC) at study entry by emailing the Multi-Institutional Team at [contact]. At the time of registration, the following documents must be submitted:

- Copy of the patient's signed and dated Informed Consent
- Patient Enrollment From
- Eligibility Checklist including source documents to verify eligibility

The VICC Coordinating Center will assign sequence numbers to all patients in screening. Sequence numbers will not be re-used if a patient screen fails.

#### 6. Data Management and Monitoring

Participating institutions will be collaborating with Vanderbilt in patient accrual. Data will be collected using a centralized electronic case report form called ON-line Clinical Oncology Research Environment = Oncore (http://www.vicc.org/ct/research/oncore.php). Oncore is a highly secure, web based, cancer specific, and customizable system that provides fully integrative clinical data management and study administration capabilities developed in an ongoing collaborative effort with NCI designated Comprehensive Cancer Centers. It fully integrates study administration functionality including protocol tracking, patient registration, NCI reporting, review committee tracking, and SAE tracking, with clinical data management functionality including electronic case report forms (eCRF) design, clinical data capture, protocol and regulatory compliance monitoring. Also the system is capable in storing basic protocol information (e.g., IRB approval dates, dates for annual renewals,) and clinical trials research data. Oncore allows the investigator to define specific protocol requirements and generate data collection forms. Creation of the data collection form is done with a single button click after the parameters of an individual protocol have been specified. Oncore permits specification of study protocols, management of patient enrollment, clinical data entry and viewing, and the generation of patient or study-specific reports based on time stamping. OnCore is embedded with a comprehensive domain repository of standard reference codes and forms to promote standardization. The sources for the repository include CDUS, CTC, CDEs from NCI, ICD, MedDRA and various best practices from contributing NCI-designated Comprehensive Cancer Centers. OnCore provides several reporting features specifically addressing NCI Summary 3 and Summary 4 and other reporting requirements. Data may also be exported in a format suitable for import into other database, spreadsheets or analysis systems (such as SPSS). This system will be used to manage all VICCC clinical trials data. OnCore is maintained and supported in the VICC Clinical and Research Informatics Resource.

Specified members at each participating site will submit all pertinent regulatory documents to the Coordinating Center, who will store it in a secure location.

As the Coordinating Center, Vanderbilt has responsibilities to health authorities to take all reasonable steps to ensure the proper conduct of the study as regards to ethics, protocol adherence, integrity, validity of the data recorded on the CRFs, and adherence to regulations regarding Good Clinical Practice (GCP) and the protection of human subjects.

In accordance with applicable regulations, GCP, and Coordinating Center procedures, sites will be contacted prior to the start of the study to review with the site staff the protocol, study requirements, and their responsibilities to satisfy regulatory, ethical, and Coordinating Center requirements.

During the course of the study, the Coordinating Center will routinely monitor sites for protocol compliance, compare CRFs with individual subjects' original source documents, assess drug accountability, and ensure that the study is being conducted according to the pertinent regulatory requirements. The review of subjects' medical records will be performed in a manner to ensure that subjects' confidentiality is maintained. Monitoring visits will primarily be conducted remotely, and sites are required to provide the appropriate source documentation in order to allow for proper oversight per GCP. Investigators must agree to cooperate with the Coordinating Center to ensure that any problems detected are resolved.

The VICC DSMC meets on a quarterly basis and ad hoc to discuss data and safety monitoring of clinical trials and to oversee the VICC DSMP. Internal audits for compliance with adverse event reporting, regulatory and study requirements, and data accuracy and completion are conducted according to the VICC DSMP according to study phase and risk. The committee reviews all serious adverse events (SAE) on Vanderbilt sponsored investigator-initiated studies on a quarterly basis and provides DSMC SAE review reports to the Vanderbilt IRB.

